10.5.2 Analysis of SVR12

Outside of pregnancy, 99% of patients treated with SOF/VEL for 12 weeks obtained an SVR12. In this pilot study, we estimate that at least 9 out of the 10 chronically HCV-infected pregnant women will have a SVR12 after treatment. Participants who do not complete the treatment course or report low adherence will be excluded from the analysis.

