DNA	deoxyribonucleic acid
DSMB	Data and Safety Monitoring Board
EAE	Expedited adverse event
FDA	Food and Drug Administration
GCLP	Good Clinical Laboratory Practices
GCP	Good Clinical Practices
HBsAg	Hepatitis B surface antigen
HBV	Hepatitis B Virus
HCV	Hepatitis C Virus
HIV	Human immunodeficiency virus
IDI	In-depth Interview
INR	International normalized ratio
IoR	Investigator of Record
IRB	Institutional Review Board
ISR	Interim Study Review
VEL	Velpatasvir
SOF/VEL	Sofosbuvir/Velpatasvir
mL	Milliliter
MWH	Magee-Womens Hospital
MWRI	Magee-Womens Research Institute
NIAID	National Institute of Allergy and Infectious Disease
NIH	National Institutes of Health
OHRP	Office of Human Research Protections
PBMC	Peripheral Blood Mononuclear Cell
PK	Pharmacokinetic
PoR	Pharmacist of Record
PTID	Participant identification number
RNA	Ribonucleic acid
SAE	Serious adverse event
SOF	Sofosbuvir
SOP	Standard operating procedure(s)
SSP	Study-specific Procedures
UPMC	University of Pittsburgh Medical Center

Phase 1 Pharmacokinetic Trial of Sofosbuvir/Velpatasvir in Pregnant Women with Chronic Hepatitis C Virus Infection

PROTOCOL TEAM ROSTER

University of Pittsburgh Study Team

[name], MSc
UPMC Magee-Womens Hospital
[name]
[name]
[contact]
[contact]
Email: [contact]

[name]

Magee-Womens Research Institute
[name]
[name]
[contact]
[contact]
Email: [contact]

[name], MSc

UPMC Magee-Womens Hospital
[name]
[name]
[contact]
[contact]
Email: [contact]

[name], FAAP, FABM

UPMC Children's Hospital of Pittsburgh
[name]
[name]
Office: [contact]
[contact]
Email: [contact]

University of Colorado

[name], PhD
Skaggs School of Pharmacy and Pharmaceutical Sciences
[name]
[name]
[contact]
[contact]
Email: [contact]

Gilead Sciences Study Team

[name], MPH
Senior Medical Scientist, Liver Disease
Gilead Medical Affairs
[contact]
Email: [contact]

Phase 1 Pharmacokinetic Trial of Velpatasvir/Sofosbuvir in Pregnant Women with Chronic Hepatitis C Virus Infection

PROTOCOL SUMMARY

Short Title:	Treatment of Chronic Hepatitis C during Pregnancy with Sofosbuvir/Velpatasvir
Clinical Phase:	Phase 1
IND Sponsor:	[name], MS
Protocol Chair:	[name], MS
Sample Size:	10 women and their infants (participants who do not complete treatment or report less than 85% adherence will be replaced)

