2.2 Rationale

Pregnancy is a critical window of opportunity for HCV screening and treatment. Pregnancy may be the ideal time to provide HCV treatment due to enhanced maternal investment in neonatal health outcomes. A meta-analysis of adherence to antiretroviral therapy during and after pregnancy showed a statistically significant difference in adherence during pregnancy (75.5%) compared to the postpartum period (53.0%)²³. In a retrospective cohort study of 369 pregnant women who were HCV seropositive at our institution from 2009 to 2012, 285 (77%) were referred to hepatology for postpartum treatment, but only 71 (25%) attended the consultation and only 6 (1.6%) were treated in the first year postpartum²⁴. Furthermore, in an ongoing study of postpartum HCV treatment with SOF/VEL paired with medication-assisted treatment (MAT) at our institution, 6 (50%) of 12 enrolled participants were lost to follow-up prior to treatment completion²⁵. *Thus, pregnancy may be the ideal period for enhanced HCV treatment adherence and engagement.*

Addressing the knowledge gap: pharmacokinetic and safety studies of new antivirals in pregnancy. Significant physiologic changes occur during pregnancy that effect drug absorption, distribution, metabolism and excretion, resulting in PK changes which may have clinical consequences²⁶. For example, increased renal clearance of drugs could result in suboptimal concentrations with standard dosing for renally cleared drugs, leading to antiviral resistance or decreased efficacy²⁷. To illustrate this, some antiretroviral medications, such as atazanavir and lopinavir, require dose changes during pregnancy to achieve therapeutic drug concentrations in the late second or third trimesters²⁷. Plasma protein concentrations including alpha-1 acid glycoprotein and albumin decrease in pregnancy, potentially influencing free drug concentrations; therefore, to comprehensively evaluate the impact of these physiologic changes in pregnancy for highly protein bound drugs, assessment of both total and free drug concentrations is critical.

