5.1.2 Retention

The importance of retention will be stressed to the participant at each visit as part of protocol adherence counseling. Once a participant is enrolled, the study staff will make every effort to retain the participants in follow-up to minimize possible bias associated with loss-to-follow-up. Any participant that discontinues the study before the PK3 visit is completed or reports missing more than 1 dose per week averaged over the duration of the study will be replaced by recruiting another participant into the study. We anticipate needing to replace no more than one participant.

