9.3 General Criteria for Permanent Discontinuation of Study Medication

A participant will be permanently discontinued from medication use by the physician investigator(s) for any of the following reasons, according the HCV treatment guidelines²³:

- 5-fold or greater increase in ALT or AST at the PK1 or PK2 visit compared to baseline result (Screening visit), confirmed by immediate repeat testing
- Any increase of ALT or AST of less than 5-fold from baseline (Screening visit) at the PK1 or PK2 visit that is accompanied by any weakness, nausea, vomiting, or jaundice
- 3-fold or greater increase in ALT or AST accompanied by bilirubin $>2x$ the upper limit of normal, confirmed on immediate repeat testing
- Increase HCV RNA viral load by greater than 10-fold at PK2 visit (6-8 weeks after starting treatment)
- Participant is unable or unwilling to comply with required study procedures
- If the participant delivers prematurely (and is still on study medication) and desires to breastfeed
- Participant might be put at undue risk to their safety and well-being by continuing medication use, according to the judgment of the study investigator(s). The study investigators will consult with the independent safety physician prior to all study medication discontinuation instituted for this reason.

Any time a participant is permanently discontinued from study medication (prior to completion of the 12 week course of study medication), HCV resistance testing will be performed.

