9.4 Permanent Discontinuation in Response to Adverse Events

Grade 1 or 2

In general, a participant who develops a Grade 1 or 2 AE as defined by the DAIDS Table for Grading Adult and Pediatric Adverse Events, Version 1.0, December 2004 (Clarification dated August 2009) regardless of relationship to study medication will continue study medication use.

Grade 3

For participants who develop a Grade 3 AE as defined by the DAIDS Table for Grading Adult and Pediatric Adverse Events, Version 1.0, December 2004 (Clarification dated August 2009) that is judged by the study investigators to be unrelated to study medication, the study medication will continue. The study medication must be permanently discontinued for participants who develop a Grade 3 AE judged by a physician investigator to be related to the study medication.

Grade 4

If a participant develops a Grade 4 AE as defined by the DAIDS Table for Grading Adult and Pediatric Adverse Events, Version 1.0, December 2004 (Clarification dated August 2009) and the AE is determined to be related to study medication, then study medication must be permanently discontinued.

Any time a participant is permanently discontinued from study medication (prior to completion of the 12 week course of study medication), HCV resistance testing will be performed.

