10.3 Sample Size

To evaluate the primary objective, we estimate a desired sample size of 10 participants. In order to maintain our sample size, any participant who discontinues treatment during the 12-week treatment period will be replaced. Based on SOF/VEL prescribing information, we will have 87% power to detect a 50% decrease in VEL AUC and >99% power to detect a 2-fold increase. For power calculations we chose this degree of change in VEL AUC because the therapeutic range of SOF/VEL is quite wide and decreases in VEL AUC of up to 50% and increases of up to 2-fold are still associated with efficacy and have acceptable safety/tolerability, respectively.

The FDA does not recommend co-administration of VEL with EFV because it decreases the VEL AUC by >50% [34]. Additionally, this sample size provides an estimated power of 0.82 to detect a 25% change in the AUC of the SOF, given the reported interpatient variability of 35.6% among female patients. Power determinations were performed in SAS v. 9.4 (SAS, Cary, NC).

Any participant that discontinues the study before the PK3 visit is completed or if a participant reports missing more than 1 dose per week averaged over the duration of the study then they will be replaced by recruiting another participant into the study.

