10.4 Participant Accrual and Retention

Pregnant and chronically HCV-infected women who meet the criteria outlined in Section 5 and are interested in participating, will be enrolled into this study. Once a participant is enrolled, the study staff will make every reasonable effort to retain her for the entire study period. Any participant lost to follow-up prior to Visit 7 will be replaced.

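### SVR12 is to be analysed only in women who complete treatment and adhere; no cure rate among all treated women is planned

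*Combined protocol and SAP*

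**What the plan says.** Section 10.5.2 expects at least 9 of 10 women to reach SVR12, against 99% outside pregnancy, and then sets the analysis population: "Participants who do not complete the treatment course or report low adherence will be excluded from the analysis". It gives no second analysis set, does not define low adherence and has no rule for a missing Visit 7 result.

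The replacement rules sit elsewhere:

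- Section 10.3: "any participant who discontinues treatment during the 12-week treatment period will be replaced".
- Protocol Summary, Sample Size: "participants who do not complete treatment or report less than 85% adherence will be replaced". Sections 5.1.2 and 10.3 word the adherence limit as more than one missed dose per week on average.
- Section 10.4: "Any participant lost to follow-up prior to Visit 7 will be replaced". Visit 7 is the SVR12 visit.
- Section 5.1.2 on the expected number: "We anticipate needing to replace no more than one participant".

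Some stops are required by the protocol. Section 9.3 lists "Increase HCV RNA viral load by greater than 10-fold at PK2 visit". Under section 9.4, SOF/VEL "must be permanently discontinued for participants who develop a Grade 3 AE judged by a physician investigator to be related to the study medication", and the same applies to a related Grade 4 event.

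**The concern.** Replacement is reasonable for the primary pharmacokinetic objective, which needs women with full exposure and complete sampling. The difficulty is that the same logic carries over to SVR12 with nothing beside it. Exclusion depends on events after treatment starts, whatever their cause, and some of those events (a viral rise, a drug-related adverse event, poor adherence) are linked to not being cured. A woman stopped for a viral rise would leave the denominator of the cure rate, and another woman would take her place.

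Section 2.5 says the study should show whether treatment response is similar to that in nonpregnant women. Table 2 in section 2.4.1, the detailed nonpregnant reference, keeps failures in its Other column in the denominator. A rate in completers only is not like for like with it. The team's earlier ledipasvir/sofosbuvir trial kept the two populations apart: section 2.2 reports pharmacokinetics in 8 women, after one was left out for suspected dosing errors, but cure in all 9.

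**Working it through.** **The plan's own figure.** With a true rate of 0.99 and n = 10, the expected count is 9.9, and P(at least 9) = 10 × 0.99⁹ × 0.01 + 0.99¹⁰ = 0.996. The projection of at least 9 of 10 agrees with its input.

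**The nonpregnant reference.** The rows of Table 2 sum to 1035 treated, 1015 SVR12, 13 virologic failures after treatment, 0 on treatment and 7 Other. With everyone counted, 1015/1035 = 98.1%. Without the Other column, 1015/1028 = 98.7%. At 98.1%, P(at least 9 of 10) = 0.985.

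**Effect of restoring excluded women.** Let x of 10 analysed women be cured and r be the number of replaced women. If none of the r is cured, the all-treated rate is x/(10 + r). Intervals are exact (Clopper-Pearson) 95%.

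| r | x = 10 | x = 9 |
|---|---|---|
| 0 (as planned) | 10/10 = 100% (69.2 to 100) | 9/10 = 90% (55.5 to 99.7) |
| 1 | 10/11 = 90.9% (58.7 to 99.8) | 9/11 = 81.8% (48.2 to 97.7) |
| 2 | 10/12 = 83.3% (51.6 to 97.9) | 9/12 = 75.0% (42.8 to 94.5) |

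Under the plan the reported rate stays in the first row whatever r is. If the one replaced woman is cured, the all-treated result is 11/11 (71.5 to 100) or 10/11, so there is no upward bias.

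**How likely a replacement is.** The protocol gives no completion rate for this regimen in pregnancy, so the rate p is an assumption. Recruiting until 10 women complete gives a negative binomial count of replacements: mean 10(1 − p)/p, P(at least 1) = 1 − p¹⁰, P(at least 2) = 1 − p¹⁰ − 10(1 − p)p¹⁰.

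| Assumed p | Mean | P(≥1) | P(≥2) |
|---|---|---|---|
| 0.95 | 0.53 | 40% | 10% |
| 0.90 | 1.11 | 65% | 30% |
| 0.80 | 2.50 | 89% | 68% |

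The 0.90 borrows the clinic visit retention in section 5.1.1. The 0.95 and 0.80 bracket it.

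**Adherence limit.** Taking the study duration as the 12 treatment weeks, there are 84 doses. Missing 12 gives 72/84 = 85.7%, and missing 13 gives 71/84 = 84.5%. Below 85% and more than one missed dose per week are therefore the same rule, and 10.5.2 can cross-refer to it.

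**The case against.** The strongest reply is that 10.5.2 follows the objective. Section 3.2 times SVR12 from completion of 12 weeks of treatment, and the viral-load question in 2.5 is largely about antiviral effect under full exposure. All 13 virologic failures in Table 2 came after treatment. A woman who completes, adheres and then relapses still counts as a failure under 10.5.2, so relapse from low drug exposure is not hidden. This stands, and it justifies keeping a completer rate. It does not justify reporting that rate alone.

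On the comparator, the 99% in 10.5.2 is closer to 98.7% than to 98.1%, so it may itself leave out the Other failures; its source is not stated. The text of 2.4.1 also gives 12 such failures where the table sums to 7. Neither point supplies the missing all-treated rate.

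On likelihood, the institution's postpartum study, in which "6 (50%) of 12 enrolled participants were lost to follow-up prior to treatment completion", is cited in section 2.2 as a contrast to pregnancy. The 90% is visit retention at one clinic. The nearest experience is the team's antenatal trial, where all nine women had a cure result. That is fair, but 9 of 9 has an exact lower 95% limit of 0.025^(1/9) = 66%, so it does not rule out any value of p used above. Virologic or adverse-event stops are indeed unlikely: Table 2 shows none of the first, and section 2.4.1 reports 2 discontinuations for adverse events in 1035. Ordinary loss or low adherence is the realistic route.

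Replacement is also not the same as exclusion. Section 10.5.2 does not expressly drop a woman who finishes treatment and is then lost before Visit 7. It gives no rule for her, while 10.4 replaces her.

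Finally, SVR12 is secondary, has no test or decision rule, and the intervals overlap heavily. That limits the weight of the point without answering it.

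**Conclusion.** The concern holds. The stated rule yields a cure rate among completers only, and no all-treated rate is planned. The bias is upward whenever excluded women are cured less often than completers. At the protocol's anticipated maximum of one replacement it is about 8 to 9 percentage points (100% to 90.9%, or 90% to 81.8%), if that woman is not cured. It is nil if nobody is excluded. The chance of at least one replacement is 40% to 89% over assumed completion rates of 95% down to 80%. The primary pharmacokinetic analysis is unaffected. This should be fixed, but it does not threaten the study's main result.

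**What to change.** 1. In 10.5.2, report SVR12 for all women who took at least one dose, including those replaced under 5.1.2, 10.3 or 10.4. Use HCV RNA 12 weeks after each woman's own last dose. Count a missing Visit 7 result as not SVR12, state how many are missing, and give the exact 95% CI.
2. Present this beside the completer and adherent rate that matches section 3.2.
3. Define low adherence in 10.5.2 by cross-reference to the existing replacement threshold.
4. List each woman left out of the completer rate, with her reason for stopping and last HCV RNA.
5. Align the SVR12 wording in the Protocol Summary, 3.2 and 4.2 so that both rates are covered. State in 10.3 and 10.4 that replacement does not remove a treated woman from the all-treated estimate.

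The cost is wording and a protocol amendment, which needs IRB approval under 13.1. No visit, assay or treatment rule changes: section 7.5 already asks women who stop to complete remaining visits, 7.4.4 times Visit 7 from the last dose and includes HCV RNA, and section 9 has discontinuations recorded on case report forms. There are two downsides. The all-treated rate may look less favourable, and counting missing results as failures is conservative, which is why the number missing should be shown.

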10.5.3 Analysis of Safety Endpoints

Rates of abnormal safety laboratory assessments will be compared to those reported in the literature on historic controls and rates of adverse pregnancy outcomes will be compared to historic HCV-infected pregnant women who have delivered at our institution. Statistical significance will be determined by chi-square test.

Qualitative Analysis

Following transcription of the IDIs, the Qual EASE team will develop a qualitative codebook using an editing approach to ensure that all relevant topics and themes are represented. Two trained qualitative coders from Qual EASE will then be trained in the codebook. A primary coder will code all interviews in the pre- and post-treatment interview groups, and a secondary coder will code half of the interviews in the pre- and post-treatment interview groups. Coding will be completed using Atlas.ti software, which will help to determine the frequency and prevalence of the topics and themes which were discussed. Cohen's Kappa scores will be calculated to determine intercoder reliability.

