Preliminary data: Our Phase 1 trial of ledipasvir/sofosbuvir (LDV/SOF) treatment in pregnancy has promising preliminary results. Between June 2017 and October 2018, 9 pregnant women between 23-24 weeks' gestation with chronic genotype 1 HCV infection were treated with LDV 90mg- SOF 400mg daily for 12-weeks. Three intensive PK visits were performed at 25-26, 29-30, and 33-34 weeks' gestation. Plasma was collected pre-dose, 0.5, 1, 2, 3, 4, 5, 8 and 12 hours post-dose to measure LDV, SOF and GS-331007 (the inactive metabolite of SOF) by

validated HPLC-MS/MS methods²⁸. Of 29 women screened, 20 were excluded due to genotype 2 or 3 infection (n=10), ongoing illicit drug use (n=4), declining participation (n=3), intention to deliver off-site (n=2), and an APRI score of >1 (n=1). All 9 women enrolled were white, with a median age of 31 years. Our published data documented that 93% of pregnant women having HCV at our institution are white²⁹. Eight women were HCV infected due to intravenous drug use (4 receiving opioid pharmacotherapy) and one was perinatally infected. All nine (100%) participants were cured and there were no adverse events greater than grade 2 related to LDV/SOF³⁰. There were no significant differences found between the PK parameters at each gestational age timepoint.

Although there are significant physiologic differences between pregnant and non-pregnant women, there are minimal differences between the second and third trimesters of pregnancy³¹. For example, the glomerular filtration rate is increased 37% in the second trimester and 40% in the third trimester³². Therefore, PK parameters were averaged across the three visits and compared between participants and non-pregnant women from regulatory trials of LDV/SOF. The geometric mean ratios and corresponding 90% confidence intervals are shown in Table 1. *Similar LDV and SOF, but lower GS-331007 exposures were observed between pregnant and non-pregnant women. All nine participants (100%) were cured. There were no adverse events related to LDV/SOF greater than grade 2. One-year follow-up of infants is on-going, and all remain HCV negative.*

Table 1: Sofosbuvir, GS-331007, and Ledipasvir Exposure in HCV-Infected Pregnant women Compared to Non-Pregnant Women

PK Parameter Mean (%CV)		HCV-infected Pregnant Women (N=8)**	HCV-infected Non-Pregnant Women (N=43)***	%GMR (90%CI)
SOF	AUC _{tau} (hr*ng/mL)	1840 (15.2)	2210 (49.9)	92.0 (78.8, 107)
	C _{max} (ng/mL)	1290 (29.3)	1640 (47.8)	89.0 (68.6, 115)

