Hepatitis B virus (HBV) reactivation has been reported in HCV/HBV coinfecting patients who were undergoing or had completed treatment with HCV direct acting antivirals, and who were not receiving HBV antiviral therapy. Some cases have resulted in fulminant hepatitis, hepatic failure, and death. Cases have been reported in patients who are HBsAg positive and also in patients with serologic evidence of resolved HBV infection (i.e., HBsAg negative and anti-HBc positive). We will exclude participants that are anti-HBc positive for this reason. Additionally, postmarketing cases of symptomatic bradycardia and cases requiring pacemaker intervention have been reported when amiodarone is coadministered with a sofosbuvir-containing regimen. Additionally a fatal cardiac arrest occurred in a patient taking amiodarone that was co-administered with sofosbuvir. For this reason, we will exclude participants who are taking amiodarone³⁴.

Laboratory abnormalities:

Lipase Elevations: In ASTRAL-1, isolated, asymptomatic lipase elevations of greater than 3 times the upper limit of normal were observed in 3% and 1% of participants treated with SOF/VEL and placebo for 12 weeks, respectively; and in 6% and 3% of participants treated with SOF/VEL in ASTRAL-2 and ASTRAL-3, respectively³⁴.

Creatine Kinase: In ASTRAL-1, isolated, asymptomatic creatine kinase elevations greater than or equal to 10 times the upper limit of normal were reported in 1% and 0% of participants treated with SOF/VEL and placebo for 12 weeks, respectively; and in 2% and 1% of participants treated with SOF/VEL in ASTRAL-2 and ASTRAL-3, respectively.

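### Maternal laboratory abnormalities are tested against unspecified literature controls that are not pregnancy-matched; with nonpregnant controls and limits, normal pregnancy can imitate toxicity (albumin) or hide it (creatinine)

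*Combined protocol and SAP*

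**What the plan says.** Section 10.5.3 (Analysis of Safety Endpoints) makes two comparisons in one sentence. For maternal laboratory results: "Rates of abnormal safety laboratory assessments will be compared to those reported in the literature on historic controls". For obstetric outcomes: "rates of adverse pregnancy outcomes will be compared to historic HCV-infected pregnant women who have delivered at our institution". It then adds: "Statistical significance will be determined by chi-square test". For the laboratory controls it gives no source, pregnancy status or number. It also gives no cut-off for an abnormal result and no significance level.

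Other sections bear on this:

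- Section 2.2 says of pregnancy that "Plasma protein concentrations including alpha-1 acid glycoprotein and albumin decrease in pregnancy" and that "the glomerular filtration rate is increased 37% in the second trimester and 40% in the third trimester".
- Section 2.4.1 has the only laboratory abnormality rates, repeated in 13.3.1. For ASTRAL-1, "isolated, asymptomatic lipase elevations of greater than 3 times the upper limit of normal were observed in 3% and 1% of participants" on SOF/VEL and placebo respectively, with 6% and 3% on SOF/VEL in ASTRAL-2 and ASTRAL-3. Creatine kinase at or above 10 times the upper limit was seen in 1% against 0% in ASTRAL-1, and in 2% and 1% on SOF/VEL in the other two. About 40% of participants in these trials were women, and section 2.4.2 says that SOF/VEL has not been adequately studied in pregnancy.
- Creatinine and a hepatic panel that includes albumin are drawn at screening (Table 3, at 14+0 to 22+6 weeks), at PK1 and PK2 (Table 5) and at V7 (Table 8).
- Section 10.2.2 lists laboratory changes within a secondary endpoint, but 10.5.3 plans no summary of change.

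**The concern.** Comparing rates between two populations credits the drug with everything else that differs between them. Unless the literature source is a pregnant one, the largest difference here is pregnancy, and the protocol itself says that pregnancy moves two of the measured quantities. The obstetric outcomes get a pregnant, HCV-infected comparator from the same hospital; the laboratory results get no matching at all.

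Maternal safety is a secondary objective (section 3.2), and section 2.5 says there is no experience yet with this combination in pregnancy. A false albumin signal, or a renal signal missed because creatinine starts low, would go straight into the reported safety conclusion. Because source, limit and unit of counting are all open, they could also be settled after the data are seen.

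**Working it through.** **1. A figure to reproduce.** There is none. The sample size was set for pharmacokinetics ("To evaluate the primary objective, we estimate a desired sample size of 10 participants", section 10.3), and no power or expected rate is given for the laboratory comparison.

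**2. What the documents give, by analyte.**

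| Analyte | Abnormality rate given | Pregnancy effect given |
|---|---|---|
| Lipase, creatine kinase | Yes, nonpregnant trials | No |
| Albumin | No | Falls, size not stated |
| Creatinine | No | Through GFR, +37% to +40% |

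No analyte has both, so the bias cannot be sized from the documents alone. Steps 3 and 4 are illustrations under stated assumptions.

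**3. Creatinine.** Assume constant production, so that creatinine is proportional to 1/GFR.

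- Ratio to the nonpregnant value: 1/1.37 = 0.730 and 1/1.40 = 0.714.
- GFR loss that only restores the nonpregnant value: 1 − 0.730 = 27% and 1 − 0.714 = 29%.
- The fold rise needed to cross any fixed nonpregnant limit is 1.37 to 1.40 times larger.
- Example: take a limit of 1.4 (the screening exclusion value in section 5.3, which states no unit and is not an analysis cut-off) and an assumed nonpregnant creatinine of 0.7 in the same unit. Outside pregnancy the limit is reached after a GFR loss of 1 − 0.7/1.4 = 50%. In pregnancy with GFR +40% (creatinine 0.5), it takes 1 − 0.5/1.4 = 64%.

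**4. Albumin.** Assume a nonpregnant limit, a 3% control rate in 1,035 controls, and a two-sided 0.05 level. Two of ten is then the smallest significant excess (p = 0.002 uncorrected, 0.031 with continuity correction). If pregnancy alone puts a fraction q of women below the limit, the chance of a signal with no drug effect is 1 − (1−q)^10 − 10q(1−q)^9:

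| q (assumed) | Chance of at least 2 of 10 |
|---|---|
| 10% | 26% |
| 20% | 62% |
| 30% | 85% |
| 50% | 99% |

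The result depends on the control group. With a 10% control rate (1,035 controls), three of ten are needed uncorrected and four corrected. The chance for q of 20% to 50% is then 32% to 95%, or 12% to 83%.

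**5. The chi-square test itself.** With 2/10 against 31/1,035, the expected abnormal count among the ten is 10 × 33/1,045 = 0.32, far too small for the approximation. With a 1% control rate (1,035 controls), one of ten is already significant uncorrected (p = 0.005). If the true rate in the study is also 1%, that happens with probability 1 − 0.99^10 = 9.6%. In the other direction, at a true lipase rate of 3%, no event in ten women has probability 0.97^10 = 74%.

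**6. The within-woman alternative.** Dosing starts at 23+0 to 25+6 weeks. PK1 (3 weeks ± 7 days) can be as early as 25+0, and PK2 (6 weeks ± 7 days) as late as 32+6. Screening is at 14+0 to 22+6, so gestational age differs, but both values come from the same pregnancy. On the protocol's trimester figures, GFR drifts by 1.40/1.37 = 1.02, about 2%, instead of 37% to 40%. For albumin the remaining drift cannot be sized. For a woman who completes treatment, V7 falls 24 weeks after the start, the equivalent of 47+0 to 49+6 weeks (± 4 days), so it is postpartum.

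**7. Why not the worst of the two on-treatment values.** With no drug effect, the expected maximum of two independent normal values lies 1/√π = 0.56 within-woman SD above the mean. A worst-of-two summary against one baseline value would therefore drift toward worsening by itself.

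**The case against.** The strongest reply is that the plan commits to no nonpregnant comparator. A reader might infer that the ASTRAL rates will be the control and that pregnancy changes will therefore be misread. The documents do not support that. Section 10.5.3 names no source, and section 10.5.1 says nonpregnant where it means it (although that is the only description of historical controls in the statistical section). A lack of SOF/VEL studies in pregnancy does not rule out untreated pregnant controls. Nor does any section say that abnormal will be judged by nonpregnant limits. Section 8.3.1 uses a general adult and pediatric grading table, and its examples of expected pregnancy findings name no laboratory value, but this makes nonpregnant limits likely, not certain.

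Two further readings go too far. One is that assessments means every blood draw counts separately, which would understate the standard error. The Protocol Summary and section 4.2 use the same term for the panel of tests, so draw-level counting is not specified. The other is that pregnancy-specific limits are needed for haemoglobin and alkaline phosphatase; the documents state no pregnancy effect on either.

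It is also fair to say that section 9.3 already compares ALT and AST with each woman's screening value, that an independent obstetrician takes part in the roughly monthly review (section 8.2), and that no stopping or design rule depends on this comparison in a ten-woman study. These arrangements protect the individual woman. They do not supply a planned summary, and they do not repair the rate comparison that would be reported.

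**Conclusion.** The concern holds in conditional form. The laboratory comparator is unnamed and not pregnancy-matched, and the only rates on file cover lipase and creatine kinase outside pregnancy. The misreading of albumin and creatinine follows if both the controls and the limits are nonpregnant. The direction for each comes from the protocol's own physiology. The creatinine ratio also rests on the 1/GFR assumption, and the albumin probabilities on assumed fractions and control rates, so neither predicts the trial's result. Independently of those conditions, a chi-square test of ten women against a literature rate of a few per cent cannot carry a claim of significance. The point deserves correction before analysis because maternal safety is a stated objective and a better contrast is already being collected.

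**What to change.** Rewrite the laboratory part of section 10.5.3 as follows:

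- **Main summary:** within-woman and descriptive. Give the change and a shift table from each woman's own screening value to PK1 and to PK2 separately, not to the worst of the two. Say which value is the baseline if screening tests were repeated, as section 5.2 allows.
- **V7:** show it separately, as postpartum.
- **Counting:** each woman counts once in any rate.
- **Literature comparison:** keep it descriptive, per participant, and only at the thresholds the literature used (lipase above 3 times, creatine kinase at least 10 times the upper limit of normal). Name the source and drop the chi-square claim of significance.

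The cost is a change of wording and one table, with no new visits, samples or data. The drawback, to be stated in the plan, is that screening (14+0 to 22+6 weeks) and PK1/PK2 (about 25 to 33 weeks) differ in gestational age, so some pregnancy drift remains and the change cannot be attributed to the drug alone. The clinical discontinuation criteria are not touched.
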